11.10.13. Non-ICH Listings

Non-ICH : Listings					
No.	Population	IDSL / TST ID / Example Shell	Title	Programming Notes	Deliverable [Priority]
Tolerability assessment					
28.	Safety	Non-Standard_Other_L1	Listing of irritation score assessment		IA [1], SAC [1]
Pharmacokinetics					
29.	PD	pkcl1p	Listing of GSK2646264 plasma PK Concentration-Time Data		IA[1],SAC [1]
30.	PD	pkpl1p	Listing of derived GSK2646264 plasma PK parameters		IA[1],SAC [1]
Pharmacodynamics					
31.	PD	Non-Standard_Other_L2	Listing of Allergen Challenge Parameters	Absolute and percent of inhibition to be presented. Part A + B	IA[1],SAC [1]
32.	PD	Example Non-Standard_Other_L2 modified based on endpoint.	Listing of Critical Temperature Thresholds	Absolute and change from baseline result to be presented. Part B only	SAC [1]
33.	PD	Example Non-Standard_Other_L2 modified based on endpoint.	Listing of UAS7 Scores and Subscores	Absolute and change from baseline result to be presented. Part C only	SAC [1]

CONFIDENTIAL

200196

Non-ICH : Listings					
No.	Population	IDSL / TST ID / Example Shell	Title	Programming Notes	Deliverable [Priority]
34.	PD	Example Non-Standard _Other_L2 modified based on endpoint.	Listing of Angioedema Activity Score(AAS)	Absolute and change from baseline result to be presented. Part C only	SAC [1]
35.	PD	Example Non-Standard _Other_L2 modified based on endpoint.	Listing of Dermatology Life Quality Index (DLQI)	Absolute and change from baseline result to be presented. Total score and Subscores Part C only	SAC [1]

11.11. Appendix 11: Example Mock Shells for Data Displays

Example : Non- Standard_SAFE_T1 Page x of y
Protocol : 2013N167482_01
Population : Safety

Table 3.17
Summary (Absolute and Change from Baseline) of Mean irritation score assessment

Treatment	Visit	Mean Irritation Score	Mean of change from baseline Irritation Score
GSK2646264 0.5%	XX	XX	XX
XXXX	XX	XX	XX
--	--	--	--
Placebo	XX	XX	XX

Programming Notes : [1] As required to be modified based on data and any applicable IDSL standard principals for listings

Example : Non- Standard_SAFE_T2 Page x of y
 Protocol : 2013N167482_01
 Population : Safety

Table 3.18
Assessment of Maximum Dermal Reactions and Response

Assessment	Reaction Grade	Statistic	GSK2646264 (0.5%) (N = XX)	GSK2646264 (1.0%) (N = XX)	Placebo (N = XX)
Dermal Response	1	n (%)	XX (XX.XX)	XX (XX.XX)	XX (XX.XX)
	2	n (%)	XX (XX.XX)	XX (XX.XX)	XX (XX.XX)
	-	-	-	-	-
	-	-	-	-	-
	7	n (%)	XX (XX.XX)	XX (XX.XX)	XX (XX.XX)
Any Dermal Reaction		n (%)	XX (XX.XX)	XX (XX.XX)	XX (XX.XX)
Grade 3 reaction (the mean time to get Grade 3) score ≥3 on the dermal response grading scale or a letter score of F, G, or H for other effects		n (%) (mean time (days))	XX (XX.XX) (XX.XX)	XX (XX.XX) (XX.XX)	XX (XX.XX) (XX.XX)
		n (%) (mean time (days))	XX (XX.XX) (XX.XX)	XX (XX.XX) (XX.XX)	XX (XX.XX) (XX.XX)

N: Number of subjects dosed with each treatment; n: Number of subjects with adverse event with particular reaction grade;
%: Calculated using the number of subjects treated with each treatment as the denominator (n/N*100);

Programming Notes : [1] As required to be modified based on data and any applicable IDSL standard principals for listings

Example : Non-Standard_PD_T1
 Protocol : 2013N167482_01
 Population : PD

Page 1 of X

Table 5.1
 Allergen challenge, Weal Area- Summary Statistics (Absolute and Percent of Inhibition)

Summary: Absolute

Treatment	Time	CI 95%		CI 95%		S.D	Min	Median	Max
		N	Mean	Lower	Upper				
Placebo	X	X	XXX.X	XXX.X	XXX.X	XX.XX	XXX	XXX	XXX
	X	X	XXX.X	XXX.X	XXX.X	XX.XX	XXX	XXX	XXX
	X	X	XXX.X	XXX.X	XXX.X	XX.XX	XXX	XXX	XXX
.									
GSK2646264 (0.5%)	X	X	XXX.X	XXX.X	XXX.X	XX.XX	XXX	XXX	XXX
	X	X	XXX.X	XXX.X	XXX.X	XX.XX	XXX	XXX	XXX
	X	X	XXX.X	XXX.X	XXX.X	XX.XX	XXX	XXX	XXX
.									
GSK2646264 (1.0%)	X	X	XXX.X	XXX.X	XXX.X	XX.XX	XXX	XXX	XXX
	X	X	XXX.X	XXX.X	XXX.X	XX.XX	XXX	XXX	XXX
	X	X	XXX.X	XXX.X	XXX.X	XX.XX	XXX	XXX	XXX
.									
ETC									

Programming Notes :	[1] For applicable endpoints, include parameter as either a BY parameter or as first column in the table [2] If absolute and percent inhibition fit in one table results can be unified in one table.
----------------------------	--

Example : Non-Standard_PD_T1 (Continued)
 Protocol : 2013N167482_01
 Population : PD

Page 1 of X

Table 5.1
 Allergen challenge, Weal Area- Summary Statistics (Absolute and Percent of Inhibition)

Summary: Percent of Inhibition

Treatment	Time	N	CI 95%		CI 95%		S.D	Min	Median	Max
			Lower	Upper	Lower	Upper				
Placebo	X	X	XXX.X							
	X	X	XXX.X							
	X	X	XXX.X							
				
GSK2646264 (0.5%)	X	X	XXX.X	XXX.X	XXX.X	XX.XX	XXX	XXX	XXX	XXX
	X	X	XXX.X	XXX.X	XXX.X	XX.XX	XXX	XXX	XXX	XXX
	X	X	XXX.X	XXX.X	XXX.X	XX.XX	XXX	XXX	XXX	XXX
				
GSK2646264 (1.0%)	X	X	XXX.X	XXX.X	XXX.X	XX.XX	XXX	XXX	XXX	XXX
	X	X	XXX.X	XXX.X	XXX.X	XX.XX	XXX	XXX	XXX	XXX
	X	X	XXX.X	XXX.X	XXX.X	XX.XX	XXX	XXX	XXX	XXX
				
ETC										

Programming Notes : [1] For applicable endpoints, include parameter as either a BY parameter or as first column in the table
 [2] If absolute and percent inhibition fit in one table results can be unified in one table.

Example : Non-Standard _PD_T2
Protocol : 2013N167482_01
Population : PD

Page 1 of X

Table 3.17
Change from baseline in composite total UAS7 Scores – Comparison

Treatment	N	Mean	Mean Difference vs. Placebo and CI 95% of mean difference
Placebo	x	xxx.x	
GSK2646264 (0.5%)	x	xxx.x	xx.x (xx.x, xx.x)
GSK2646264 (1.0%)	x	xxx.x	xx.x (xx.x, xx.x)

Programming Notes : [1] As required to be modified based on data and any applicable IDSL standard principals for listings

CONFIDENTIAL

200196

Example : Non-Standard _Other_L1
Protocol : 2013N167482_01
Population : Safety

Page 1 of X

Listing 28

Listing of irritation score assessment

Subject	Treatment	Visit	Irritation Score assessment
XXX	GSK2646264 (0.5%)	XX	XX
		XX	XX
--	--	--	--
XXX		XX	XX

Programming Notes : [1] As required to be modified based on data and any applicable IDSL standard principals for listings

Example : Non-Standard _Other_L2
Protocol : 2013N167482_01
Population : PD

Page 1 of X

Listing 31
Listing of Allergen Challenge Parameters

[figure not shown]
Treatment	Inv./ Subj.	Visit	Parameter (Unit)	Result	Percent of Inhibition
XXXXX	XXXXX/ XXX	XXXX	XXXXX	XXX.XX	XXX.XX
			XXXXX	XXX.XX	XXX.XX
			XXXXX	XXX.XX	XXX.XX
			XXXXX	XXX.XX	XXX.XX
			XXXXX	XXX.XX	XXX.XX
		XXXX	XXXXX	XXX.XX	XXX.XX
			XXXXX	XXX.XX	XXX.XX
			XXXXX	XXX.XX	XXX.XX

Programming Notes : [1] As required to be modified based on data and any applicable IDSL standard principals for listings

Example : Non-Standard _PD_F1
Protocol : 2013N167482_01
Population : PD

Page 1 of X

Figure 5.1
Allergen Challenge, Weal Area (Percent of Inhibition) - Individual Subject Plot

[figure not shown]

Programming Notes : [1] Plot adapted accordingly based on study data (overlaid by treatment)
[2] Subject will have two values one for treatment and another for placebo. Therefore use one colour for the subject id and two symbols for treatment (e.g. o=placebo, +=Treatment). Adapt the graph correspondingly.

Example : Non-Standard _PD_F1
Protocol : 2013N167482_01
Population : PD

Page 1 of X

Figure 5.2
Allergen Challenge, Weal Area (Percent of Inhibition) - Mean (95% CI) Plot

Programming Notes : [1] Plot adapted accordingly based on study data.
[2] Replicate this box plot to other similar plots, eg. for absolute values..

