## 2. OBJECTIVE(S) AND ENDPOINT(S)

### 2.1. Primary objectives and endpoints for all study parts (A, B & C)

Objectives	Endpoints

Safety and Tolerability
 
To investigate the safety and tolerability of topically applied GSK2646264 cream and its placebo in healthy subjects, subjects with cold urticaria (CU1) and subjects with chronic spontaneous urticaria (CsU).
	
Safety and Tolerability
 
 
Number, severity and frequency of AEs and serious AEs (local and systemic)
 
heart rate
 
blood pressure
 
12- lead ECG
 
clinical laboratory safety tests
 
assessment of the local tolerability of the study medication
 

1. All Healthy subjects and the Cold urticaria subjects should be screened for reactivity to one of the allergens used in skin prick test. (grass pollen, Dermatophagoides pteronyssinus, birch pollen and cat dander)

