### 7.1.3. Definition of Adverse Events

An AE is any untoward medical occurrence in a patient or clinical investigation subject, temporally associated with the use of a medicinal product, whether or not considered related to the medicinal product.

NOTE: An AE can therefore be any unfavorable and unintended sign (including an abnormal laboratory finding), symptom, or disease (new or exacerbated) temporally associated with the use of a medicinal product.

Events meeting the definition of an AE **include**:

- Any abnormal laboratory test results (hematology, clinical chemistry, or urinalysis) or other safety assessments (e.g., ECGs, radiological scans, vital signs measurements), including those that worsen from baseline, and felt to be clinically significant in the medical and scientific judgement of the investigator.
- Exacerbation of a chronic or intermittent pre-existing condition including either an increase in frequency and/or intensity of the condition.
- New conditions detected or diagnosed after study treatment administration even though it may have been present prior to the start of the study.
- Signs, symptoms, or the clinical sequelae of a suspected interaction.
- Signs, symptoms, or the clinical sequelae of a suspected overdose of either study treatment or a concomitant medication (overdose per se will not be reported as an AE/SAE unless this is an intentional overdose taken with possible suicidal/self-harming intent. This should be reported regardless of sequelae.).
- When skin tolerability is assessed, a “dermal scoring” of 2 or above, and a score of C, F, G or H in “other effects scoring (ii)”, will be reported as adverse event.

Events that **do not** meet the definition of an AE include:

- The disease/disorder being studied, or expected progression, signs, or symptoms of the disease/disorder being studied, unless more severe than expected for the subject's condition.
- Medical or surgical procedure (e.g., endoscopy, appendectomy); the condition that leads to the procedure is an AE.
- Situations where an untoward medical occurrence did not occur (social and/or convenience admission to a hospital).
- Anticipated day-to-day fluctuations of pre-existing disease(s) or condition(s) present or detected at the start of the study that do not worsen.

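### The SAP Table 3.18 footnote counts adverse events, not scored reactions, so the only planned count of subjects by maximum dermal grade can omit reactions that were scored but not reported as AEs

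*SAP*

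**What the plan says.** Protocol 2.1 lists "assessment of the local tolerability of the study medication" as a primary endpoint for all parts, as a separate item from adverse events. Protocol 6.3.4.1 defines the measurement: a dermal score from 0 to 7 plus one of seven letters (Z, A, B, C, F, G, H) for other effects.

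SAP 7.1.1 (Table 3) plans tolerability scores in a block of their own, apart from the AE block. SAP 11.10.6 gives them two tables:

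- Table 3.17, the mean irritation score.
- Table 3.18, titled "Assessment of Maximum Dermal Reactions and Response". Its shell in SAP 11.11 has rows for dermal grades 1 to 7, a row for any dermal reaction, a Grade 3 row, and a row defined as "score ≥3 on the dermal response grading scale or a letter score of F, G, or H for other effects". The columns are the two strengths and placebo.

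The footnote to Table 3.18 then defines the numerator as "n: Number of subjects with adverse event with particular reaction grade". The denominator is all subjects treated with that treatment.

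Protocol 7.1.3 says when a skin assessment is reported as an AE: a dermal score "of 2 or above, and a score of C, F, G or H in" the other-effects scale. That rule is one bullet in a list introduced by "Events meeting the definition of an AE" and the word include.

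**The concern.** The footnote and the table describe different quantities. The title and rows ask for each subject's worst score on the irritation scale. The footnote asks for subjects who had an AE of that grade. The two agree only if every scored reaction is also an AE, and Protocol 7.1.3 does not require that.

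A programmer who follows the footnote would filter on the AE record. Whether a reaction appears would then depend on AE reporting as well as on the scale, and the absolute counts could only fall. Localised AEs already have their own table (3.4), so an AE-based Table 3.18 would partly repeat it and leave the separate primary endpoint without a count by grade.

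The groups are small. With 9 subjects in each Part A dose group (Protocol 4.1), one omitted subject moves a column percentage by 1/9 = 11.1 points, if the column holds that group alone.

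**Working it through.** The plan gives no figure to reproduce. The check is which scores the AE rule captures, compared with which scores the table's rows need.

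**Inputs.** Dermal scores 0 to 7 (8 values) and letters Z, A, B, C, F, G, H (7 values), from Protocol 6.3.4.1. The AE rule is from Protocol 7.1.3. The rows are from the Table 3.18 shell. The shell does not define the any-reaction row; I take it as a dermal score of 1 or more.

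**Two readings of the AE rule.**
- Literal: dermal score at least 2 *and* letter C, F, G or H.
- Looser: each is a separate trigger, so dermal score at least 2 *or* letter C, F, G or H.

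**Counts of possible score pairs.**
- All pairs: 8 × 7 = 56. Pairs with dermal score at least 1: 7 × 7 = 49.
- Literal rule: 6 grades (2 to 7) × 4 letters = 24 pairs, all with dermal score at least 1. Not captured: 49 − 24 = 25, made up of 7 pairs at grade 1 and 6 × 3 = 18 pairs at grades 2 to 7 with Z, A or B.
- Looser rule, dermal score at least 1: 6 × 7 = 42 pairs at grades 2 to 7, plus 4 at grade 1 (with C, F, G or H) = 46. Not captured: 3 (grade 1 with Z, A or B).
- Row for score at least 3 or letter F, G or H: 5 × 7 = 35 pairs, plus 3 × 3 = 9 at scores 0 to 2 with F, G or H, giving 44. The literal rule captures 5 × 4 + 3 = 23; the looser rule captures all 44.

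| Row of Table 3.18 | Pairs belonging by score | Captured, literal rule | Captured, looser rule |
|---|---|---|---|
| Grade 1 | 7 | 0 | 4 |
| Each of grades 2 to 7 | 7 | 4 | 7 |
| Any dermal reaction | 49 | 24 | 46 |
| Score at least 3, or F/G/H | 44 | 23 | 44 |

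These counts show which parts of the scale the skin-score rule covers. They are not expected event rates.

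**Do other displays supply the missing count?**
- Table 3.17 gives means, not numbers of subjects, and SAP 11.4.3 caps the combined score at 3, so it cannot separate grades 3 to 7.
- Listing 28 (SAP 11.10.13) shows irritation scores by subject and visit with no AE filter, but does not summarise them.
- Table 3.4 counts localised AEs.

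No other planned table counts subjects by maximum dermal grade.

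**Does the SAP's basis on an older protocol explain the mismatch?** The SAP cites Amendment 2. The log in Protocol Appendix 8 shows no change to 7.1.3, so this does not appear to be the cause.

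**The case against.** The strongest reply is that the footnote is stray AE-template wording in an example shell. Everything else about the table is score-based, SAP 11.4.3 describes tolerability through the scale with no AE filter, and a programming note allows the shell to be modified. A sensible programmer might ignore the footnote. The template origin is plausible, but it is an inference. The note allows changes to fit the data; it does not redefine n, and no other section does. The footnote is the only stated counting rule for the table.

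A second reply is that the scores survive. They do: Listing 28 holds them, and in groups this small the counts by grade could be rebuilt by hand. That limits the harm without making the table correct.

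Three stronger readings are tempting, and the documents do not support them.

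- A reader might infer that the grade 1 row must always be zero. The skin-score bullet is one item in an inclusive list. Under 7.1.3 an investigator may also report a safety finding "felt to be clinically significant in the medical and scientific judgement of the investigator". A grade 1 reaction can become an AE that way, as can a more severe one with letter Z. On the looser reading, grade 1 with C, F, G or H is an AE under the skin-score rule itself.
- A reader might turn 25 of 49 pairs into a claim that about half of reactions are lost. That gives every score pair equal weight, though the documents give no frequencies, and it holds only on the literal reading. On the looser reading the figure is 3 of 49. Protocol 5.5.1 words the tolerability part of its dose-limiting toxicity definition in a similar way, so the literal reading cannot be ruled out either.
- A reader might infer that the active cream is made to look better than placebo. The footnote applies to every column alike, and nothing in the documents shows a difference in AE reporting between treatments. Only the absolute counts are shown to be at risk.

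**Conclusion.** The footnote is inconsistent with the table it defines and with local tolerability being a primary endpoint separate from AEs. Followed as written, it drops scored reactions not reported as AEs from the only planned count of subjects by maximum dermal grade.

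Under the 7.1.3 skin-score rule, grade 1 with letter Z, A or B is exposed on either reading. On the literal reading, grade 1 with any other letter and grades 2 to 7 with Z, A or B are exposed as well. In each case the reaction is lost only if the investigator does not report it as an AE by another route.

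The number of subjects affected cannot be derived from the documents. It depends on the score distribution, on which reading of 7.1.3 the sites apply, and on their AE reporting. Any error in the counts is downward. It is recoverable, because the raw scores are listed. This is a modest but definite error in a stated counting rule, worth correcting before the table is programmed.

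**What to change.** Replace the footnote with:

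*n: number of subjects whose maximum dermal score over all tolerability assessments after the first dose (including pre-dose assessments on later dosing days) equals the stated grade, taken from the recorded irritation scores whether or not an adverse event was reported.*

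Derive the any-reaction row and the Grade 3 rows from the same recorded scores, dermal and letter.

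The wording about later pre-dose checks matters. In Parts A and B tolerability is assessed before each dose and about 6 hours after it (Protocol 6.1.1 to 6.1.3). A definition limited to post-dose assessments could be read to exclude the next morning's check, which is where a reaction to the previous day's application may be seen.

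With this footnote the table no longer depends on how 7.1.3 is read. The cost is one SAP footnote and the matching programming, with no new data. The displayed counts may be higher than under the present wording.

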## 3.2. Discussion of Study Design

### 3.2.1. Design Rationale

This study is designed to evaluate the safety, tolerability, pharmacokinetics and pharmacodynamics of single and repeat ascending dose of GSK2646264 in healthy subjects (First Time in Human study), cold urticaria and chronic spontaneous urticaria subjects.

The proposed bilateral design for Part A is well established and most efficient study design in absence of any effect. In this design, each subject in Part A will be his/her own control. The subject's left and right side of the defined study body surface area will be randomised to either GSK2646264 or Placebo.

Parts B & C will be a placebo controlled randomised parallel design randomisation where subjects will receive either active or placebo study treatment, not both (unlike Part A of the study).

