## 5.4. Treatment Assignment

Subjects will be assigned to treatment in accordance with the randomization schedule generated by Parexel, prior to the start of the study. Randomisation will occur within each cohort of study. Subjects will be randomised to 1:1 to receive bilateral treatment of GSK2646264 or placebo in Part A. For Parts B & C, subjects will be randomised 3:1 active:placebo respectively, to receive either GSK2646264 or placebo.

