## 9.2. Sample Size Considerations & Statistical Analyses

There are no formal hypotheses to be tested. An estimation approach will be taken and 95% confidence intervals will be constructed to provide a range of plausible values for the comparisons of interest.

Approximately 42 subjects will be randomised in total, consisting of 18 subjects in Part A (9 subjects on first dose group and 9 subjects in second dose group), 12 subjects in Part B and 16 subjects in Part C of the study. The sample size is based on feasibility and not driven by any formal hypothesis testing.

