7. PRIMARY STATISTICAL ANALYSES

7.1. Safety Analyses

7.1.1. Overview of Planned Analyses

The safety analyses will be based on the ‘Safety’ population, unless otherwise specified.

Table 3 provides an overview of the planned analyses, with further details of data displays being presented in [Appendix 10: List of Data Displays](#).

Table 3 Overview of Planned Safety Analyses for Part A, B and C of study

Endpoint / Parameter/ Display Type	Absolute				Change from Baseline			
	Summary		Individual		Summary		Individual	
	T	F	F	L	T	F	F	L
Drug Exposure								
Exposure to Study Drug	Y				Y			
Adverse Events								
Summary of All Adverse Events	Y				Y			
Drug-Related Adverse Events	Y							

Endpoint / Parameter/ Display Type	Absolute				Change from Baseline			
	Summary		Individual		Summary		Individual	
	T	F	F	L	T	F	F	L
Summary of All Localised Adverse Events	Y							
Serious Adverse Events	Y			Y				
AEs Leading to Discontinuation	Y			Y				
AE by Maximum Intensity	Y							
Clinical Laboratory Assessments								
Clinical Chemistry	Y			Y	Y			Y
Haematology	Y			Y	Y			Y
Urinalysis	Y			Y ¹	Y			
Electrocardiogram (ECG)								
ECG Findings	Y			Y	Y			Y
ECG Values	Y			Y	Y			Y
Vital Signs								
Vital Signs	Y			Y	Y			Y
Tolerability assessment								
Tolerability scores	Y			Y	Y			Y

NOTES :

- T = Table, F = Figure, L = Listing, Y = Yes display generated.
- Stats Analysis = Represents TFL related to any formal statistical analyses (i.e. modelling) conducted.
- Summary = Represents TFL related to any summaries (i.e. descriptive statistics) of the observed raw data.
- Individual = Represents FL related to any displays of individual subject observed raw data.
- Tolerability analyses will be produced for Part A and B only.

1 Urinalysis will only list abnormal assessments

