
Tolerability will be assessed with the skin irritation scoring system for Part A and B of study, where the score consists of a numeric score according to the dermal response scoring i), and a letter according to the other effects scoring ii), as follows
 
0 = no evidence of irritation 1 = minimal erythema, barely perceptible (pink) 2 = moderate erythema (definite redness), readily visible; minimal edema or minimal papular response 3 = strong erythema (intense redness), or erythema and papules 4 = definite edema 5 = erythema, edema, and papules 6 = vesicular eruption 7 = strong reaction spreading beyond test site
 
ii) Other effects:
 
Z = no other effect A = slight glazed appearance B = marked glazing C = glazing with peeling and cracking F = glazing with fissures G = film of dried serous exudate covering all or part of the patch site H = small petechial erosions and/or scabs
 
For each skin assessment, letter grade will be converted to numeric values as below: A=0, Z=0, B=1, C=2, F=3, G=3, H=3. A combined score for each subject will be calculated by adding all numeric and letter scores. A maximum score of 3 is allowed. Mean irritation score for each subject will be computed through the study period. Mean score will be analyzed.

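### The Part A tolerability tables set each strength beside one placebo group pooled over both dose groups, with no within-subject summary

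*SAP*

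**What the plan says.** Protocol 3.2.1 gives the reason for the bilateral layout: "In this design, each subject in Part A will be his/her own control". Protocol 5.4 allocates accordingly: "Subjects will be randomised to 1:1 to receive bilateral treatment of GSK2646264 or placebo in Part A". Protocol 9.2 gives the size as "18 subjects in Part A (9 subjects on first dose group and 9 subjects in second dose group". Group 1 uses the 0.5% cream and group 2, in different subjects, the 1.0% cream. Among the primary endpoints in Protocol 2.1 is "assessment of the local tolerability of the study medication".

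Two SAP tables summarise that endpoint, and both have shells in Appendix 11. Table 3.18 has columns for 0.5%, 1.0% and one Placebo. Its footnote reads "N: Number of subjects dosed with each treatment", and it defines the percentage on that count: "Calculated using the number of subjects treated with each treatment as the denominator (n/N*100". Table 3.17 (mean irritation score by visit) has an abbreviated shell that lists treatments as rows and ends in one Placebo row. SAP 11.3.1 has a single placebo code. The display list in SAP 11.10.6 names no split by dose group, side or BSA for either table.

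SAP 11.4.3 defines the score without mentioning body side: "A combined score for each subject will be calculated by adding all numeric and letter scores". Protocol 9.3.2.1 says local skin reactions will be summarised by strength, where possible, and by BSA. It also says that safety data get no formal statistical analysis.

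**The concern.** Most safety tables in the SAP are restricted to a Total column. Tables 3.17 and 3.18 are not, so their use is to let a reader set active beside placebo. In Part A the natural placebo for a strength is the other side of the same nine subjects. The shell instead offers a placebo group of which half comes from the other dose group.

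The two sets of placebo sides were not treated alike. Group 1 had three daily applications to the arms, at 0.2%, 1% and 5% BSA. Group 2 had four dosing days on a small arm area and the torso, starting at about 5% BSA. (For Days 3-4 of group 2, Protocol Table 3 gives about 5% per side and SAP Tables 11 and 12 give 10%; these passages need reconciling, but the groups differ either way.) Table 3.18 reports the maximum grade, which can only rise with more assessments.

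If group 2 has more background reactions, 1.0% looks worse against pooled placebo and 0.5% looks better, which resembles a strength effect. Separately, marginal percentages cannot show whether the same subjects reacted on both sides, which would suggest the vehicle or sensitive skin, or whether different subjects reacted on each side.

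**Working it through.** **The plan's own Part A figure.** The documents give no precision or rate for tolerability. The only computed Part A design figure is in Protocol 9.2.1: a 95% half-width of 18.5 for weal-size inhibition with n = 9 and SD 24. It reproduces as t(0.975, 8 df) × SD / √9 = 2.306 × 24 / 3 = 18.45. It concerns another endpoint, but it confirms planning on one within-subject value for each of nine subjects.

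**Column counts in Part A.** N is the number of subjects dosed with each treatment, so 0.5% has 9, 1.0% has 9, and placebo has 9 + 9 = 18. For either strength, 9/18 = 50% of the placebo column comes from other subjects.

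**Effect of pooling.** Let a1, p1 be the active and placebo rates in group 1, and a2, p2 those in group 2. With equal group sizes the pooled placebo rate is (p1 + p2)/2. Then:

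- 0.5% against pooled placebo = (a1 − p1) − (p2 − p1)/2
- 1.0% against pooled placebo = (a2 − p2) + (p2 − p1)/2

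The shift is half the gap between the groups' placebo rates, with opposite signs. It is zero if p1 = p2.

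**Illustration (assumed counts).** Take placebo reactions in 1/9 and 4/9 subjects, and active reactions in 2/9 and 5/9. The within-group difference is +11.1 points for both strengths. Pooled placebo is 5/18 = 27.8%, so the displayed differences are 22.2 − 27.8 = −5.6 points for 0.5% and 55.6 − 27.8 = +27.8 points for 1.0%.

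**Size from dosing days alone (assumed daily rates).** Suppose no drug effect, and a background chance q of a reaction on each dosing day, independent between days. The maximum-grade rate is 1 − (1 − q)^3 in group 1 and 1 − (1 − q)^4 in group 2.

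| q | 3 days | 4 days | Shift (half the gap) |
|---|---|---|---|
| 5% | 14.3% | 18.5% | 2.1 points |
| 10% | 27.1% | 34.4% | 3.6 points |
| 20% | 48.8% | 59.0% | 5.1 points |

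The shift is added for 1.0% and subtracted for 0.5%. This covers the number of days only; any effect of site or area is not included.

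**Loss of pairing.** Suppose one group shows active 5/9 and placebo 2/9. The number reacting on both sides can be 0, 1 or 2, so the discordant split (active only : placebo only) can be 5:2, 4:1 or 3:0. The margins do not say which. This holds even if the placebo column is split by group, so splitting alone is not enough.

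**The case against.** The strongest reply is that these are example shells, marked as open to modification, and that no sentence says placebo will be pooled. That is true. Pooling is inferred from the single column, the definition of N and the single placebo code. It is clear for Table 3.18 and less so for Table 3.17, whose shell is abbreviated. The protocol's commitment to summarise by BSA would separate much of the two groups' data, but neither shell carries BSA. The licence to modify names no split and no pairing.

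Other replies also stand. Listing 28 is laid out by subject, treatment and visit, so with nine subjects per group the pairs can be read by hand; the gap is in the summary tables. The assumed shifts are small: 5.1 points is less than half of one subject in nine (11.1 points), and the standard error of a 34% rate at n = 9 is about 16 points. No section ties dose progression to Table 3.18, and Protocol 3.2.2.4 has already fixed 1% for Parts B and C.

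Three stronger readings are tempting.

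- **A primary comparison is biased.** The documents plan no test or interval for safety; the contrast is descriptive.
- **Pooling itself destroys the pairing.** It does not; the marginal percentages do.
- **Parts A and B are merged in one table, with much larger distortion.** SAP 7.1.1 says only "Tolerability analyses will be produced for Part A and B only". The display list does not mark Tables 3.17 and 3.18 as combining the parts, and both are also due at the interim after Part A alone. The SAP was written for a bilateral Part B, whereas the current protocol has 9 active and 3 placebo in parallel, so any figure for a merged table depends on which design is assumed.

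**Conclusion.** The point holds as a fault of display for a primary endpoint. As shelled, Table 3.18 places each Part A strength beside a placebo group of which half is other subjects' skin, and it contains no within-subject summary although the design makes each subject the control. Table 3.17 points the same way, but it is by visit, so the maximum-grade calculation does not apply to it.

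The exact result is the half-gap rule, which needs only equal group sizes. The range of about 2 to 5 points rests on assumed daily rates of 5% to 20%, independence between days and no drug effect. The true shift could be zero, or larger if site or area matters. The change is worth making for the final report, because the groups differ in ways that prevent assuming equal placebo rates. It does not call any formal analysis or recorded decision into question.

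**What to change.** For Part A, lay out Tables 3.17 and 3.18 by dose group: 0.5% beside the placebo side of the same nine subjects, and 1.0% beside the placebo side of its own nine. In Table 3.18 add, for each dose group, the number of subjects whose active side scored higher than, equal to or lower than their placebo side. State in SAP 11.4.3 that the score is taken per subject and treated side.

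Present Part B in its own tables, as parallel active and placebo groups under the current protocol. A paired 95% interval (8 df) for the mean irritation difference is optional; on a score capped at 3 in nine subjects it adds little.

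The cost is SAP text, shells and programming. Listing 28 already plans scores by subject and treatment, so no new assessment should be needed, although the eCRF is not among the documents. The downside is more columns, and a placebo N of 9 per comparison instead of 18.
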